### **3.2 Exclusion Criteria**

3.2.1 Patients with documented HER2-positive metastatic disease are not eligible, even if their primary breast cancer was HER2-negative.

3.2.2 Patients who have received prior anti-cancer therapy (e.g., biologic or other targeted therapy, chemotherapy) within 2 weeks prior to registration. Hormone therapy is permitted until registration.

*Note: patients who received prior anti-PD-1, PD-L1 or PD-L2 agents are still eligible. A wash-out period of 2 weeks prior to registration is required.*

3.2.3 Patients who have received prior capecitabine therapy are not eligible.

3.2.4 Patients who have not recovered from adverse events to Grade 1 severity or lower due to agents administered more than 2 weeks earlier than registration, are not eligible, except for stable sensory neuropathy ( $\leq$  Grade 2) and alopecia.

3.2.5 Patients who have received radiotherapy  $\leq$  4 weeks prior to registration, with the exception of palliative radiotherapy, who have not recovered from side effects of such therapy to baseline or grade  $\leq$  1 are not eligible for participation.

*Note: any lesions treated with radiation therapy cannot be used in disease assessment.*

3.2.6 Patients who have undergone major surgery  $\leq$  4 weeks prior to registration or have not recovered from side effects of such procedure are not eligible for participation.

3.2.7 Patients may not be receiving any other investigational agents.

*Note: A wash-out period of 2 weeks prior to registration is required for any patient to be enrolled in the study.*

3.2.8 Patients who have a history of allergic reactions or hypersensitivity reactions attributed to compounds of similar chemical or biologic composition to pembrolizumab and/or humanized antibodies are not eligible.

3.2.9 Known hypersensitivity to capecitabine, fluorouracil, or any component of the formulation.

3.2.10 History of autoimmune disease, including but not limited to myasthenia gravis, myositis, autoimmune hepatitis, systemic lupus erythematosus, rheumatoid arthritis, inflammatory bowel disease, vascular thrombosis associated with antiphospholipid syndrome, Wegener's granulomatosis, Sjogren's syndrome, Guillain-Barre syndrome, multiple sclerosis, vasculitis or glomerulonephritis.

- Patients with history of autoimmune-related hypothyroidism on a stable dose of thyroid replacement hormone may be eligible for this study.
- Patients with controlled Type I diabetes mellitus on a stable dose of insulin regimen for more than a month may be eligible for this study.

- Patients with auto immune disease that does not recur unless patient is exposed to an external trigger (i.e. gluten and celiac disease) may also be eligible.

- 3.2.11 Patients who have evidence of active, noninfectious pneumonitis or have a history of severe pneumonitis that required treatment with steroids are not eligible for this study.  
*(Note: Replacement physiologic dose of steroids (prednisone 10 mg daily or equivalent) are allowed)*
- 3.2.12 Patients who have an uncontrolled intercurrent illness including, but not limited to any of the following, are not eligible:
- Hypertension that is not controlled on medication (defined as  $\geq 140/100$  at rest, average of 3 consecutive readings)
  - Ongoing or active infection requiring systemic treatment
  - Symptomatic congestive heart failure
  - Unstable angina pectoris
  - Cardiac arrhythmia
  - Psychiatric illness/social situations that would limit compliance with study requirements
  - Known positive test for HIV
  - Has known active Hepatitis B (e.g., HBsAg reactive) or Hepatitis C (e.g., HCV RNA [qualitative] is detected).
  - Active tuberculosis
  - Prior allogeneic bone marrow transplantation or solid organ transplant
  - Administration of a live, attenuated vaccine within 4 weeks before starting the study treatment or anticipation that a live attenuated vaccine will be required during the study.
  - Any other illness or condition that the treating investigator feels would interfere with study compliance or would compromise the patient's safety or study endpoints
- 3.2.13 Female patients who are pregnant or nursing (lactating) are not eligible.
- 3.2.14 Patients exhibiting any other condition that would, in the Investigator's judgment, preclude patient's participation in the clinical study due to safety concerns or compliance with clinical study procedures are not eligible for participation. This might include, but is not limited to, infection/inflammation, intestinal obstruction, and/or social/psychological complications.
- 3.2.15 Patients with impaired GI function or GI disease that may significantly alter absorption of oral capecitabine (e.g. ulcerative disease, uncontrolled nausea, vomiting, diarrhea, malabsorption syndrome or small bowel resection) are not eligible for participation.
- 3.2.16 Patients with a history of another malignancy that progressed or required treatment within the past year prior to registration are not eligible for participation. Note: the exceptions to this include non-melanoma skin cancer or excised carcinoma in situ of the cervix.

## 4.0 TREATMENT PLAN

### 4.1 Overview

This will be an open-label, single-arm, phase II study of the combination of pembrolizumab and capecitabine in locally advanced and metastatic triple negative and hormone-refractory breast cancer.

Pembrolizumab will be administered at 200mg IV on Day 1 of each cycle (1 cycle=21 days).Capecitabine will be administered at 1000 mg/m^2 BID D1-14q21d. Patients will be instructed to take the morning dose of capecitabine before coming to clinic for pembrolizumab infusion. (Refer to section 8.2.5 for details about drug intake). Patients will continue to receive treatment until disease progression or unacceptable toxicity. After discontinuation of study drugs, patients will be assessed every 3 months up to 1 year for PFS, with visits and/or phone calls.

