#### 4.2.2 Capecitabine

Capecitabine is to be self-administered by patient, 1000 mg/m^2 PO BID Days 1-14 every 21 days. It is to be taken preferably 12 hours apart (with minimum 8 hours between doses).It is to be ingested with food or within 30 minutes of eating with 8 oz glass of water (not fruit juices). Tablets are to be swallow whole and not crushed or cut. No supportive medications are required as part of this study.

If dose is missed and next dose would normally be in less than 8 hours, then dose should be skipped entirely and marked accordingly on the medication diary (available as stand-alone document).

Patients will also record doses taken, missed, or skipped, as well as any

occurrence of vomiting, diarrhea, increased stool frequency, or rashes on the Medication Diary. This Diary will be reviewed by a member of the study team at every study visit, and any issues with compliance will be addressed. Along with the diary, patients should bring the medication bottle and any remaining tablets with them on each study visit. The Coordinator and PI will monitor for compliance. If a patient misses more than 7 consecutive doses of capecitabine due to poor adherence, the patient will be removed from study treatment. If capecitabine doses are missed, and it is < 7 doses, they may be made up within the same cycle. Patients will be given 14 days of supply at the start of study treatment. Additional capecitabine tablets will be dispensed every 3 weeks. The consent form will also ask that patients agree to keep the capecitabine pills out of reach from children and other individuals in their home.

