**Capecitabine Dose Modifications:**

**Table 2: Hematologic Toxicities**

ANC(/mm  )		Platelets (/mm  )	Modification
<1000/mm 	AND/OR	<100,000/mm 	Hold until ANC ≥ 1000/mm  and PLt ≥ 100,000  resume at 20% dose reduction
≥1000/mm 	AND	≥100,000/mm 	No dose modification

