**Table 3: Mucositis, Diarrhea or Esophagitis**

Grade	Toxicities/Symptoms	Modification
1	Mucositis, esophagitis, or diarrhea	No dose modification
2	Diarrhea	No dose modification
2	Mucositis, or esophagitis	Hold until ≤ grade 1 and resume at 20% dose reduction
3	Diarrhea	Hold until ≤ grade 1; resume at 20% dose reduction
3/4	Mucositis or esophagitis	Hold until ≤ grade 1; resume at 20% dose reduction

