**Table 4: Palmar-Plantar Erythrodysesthesia Syndrome (Hand and Foot Rash)**

Grade	Modification
1	No dose modification
2	Hold until symptoms resolve to grade 0 or 1 Resume a 20% dose reduction ( per treating physician's discretion )
≥3	Hold until symptoms resolve to Grade 1 or lower. Resume with dose reduction of 1 level (20% dose reduction).

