 A baseline tissue biopsy of a metastatic site will be obtained for PD-L1 immunohistochemical (IHC) assessment, from all patients. An archived specimen may be used (metastatic tissue only) if collected no more than 2 months prior to registration. Otherwise fresh biopsy of metastatic lesion is mandatory at baseline and should be performed no more than 2 months prior to registration. The requirement for biopsy (fresh) may be omitted per treating physician's discretion, if the biopsy would cause undue morbidity to the patient and if enough tissue from a prior metastatic lesion (archival biopsy) is not available.

PD-L1 IHC assay from QualTek will be used for the study.  
Please refer to section 9.1 and laboratory manual for more details

 Hematology will include white blood cells (WBC) with differential, platelet count, hematocrit, and hemoglobin. To be performed within 14 days before Day1

 Serum Chemistry will include calcium, chloride, creatinine, sodium, potassium, blood urea nitrogen, bicarbonate, glucose, total bilirubin, aspartate aminotransferase (AST), alanine aminotransferase (ALT), alkaline phosphatase (ALP), albumin, and total protein. To be performed within 14 days prior to registration. Patients with liver metastasis will have additional liver function testing done on C1D7 and C1D14, which can be done locally and sent to NU for review.

 This is to be done if the patient is required to have a biopsy (in order to test for bleeding parameters before biopsy). It is to be performed and resulted before the biopsy. (Also refer to footnote 14)

 Serum or urine test for females of child-bearing potential.

 Pembrolizumab will be administered IV at the assigned dose, at Day 1 of every cycle (1cycle =21 days)

 Capecitabine will be self-administered orally by patients at a fixed dose daily on Days 1-14 twice daily, of each cycle.

 A cycle is defined as 21 days (+/- 3 days).

 Patients will be assessed every 3 months up to 2 year after discontinuation of the study drugs for PFS with visits and/or phone calls.

 concomitant medications to be recorded during screening, at the beginning of each cycle and for 30 days after end of treatment

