Thyroid function will be evaluated at baseline (performed within 14 days of Day1) and prior to the start of the next treatment cycle e.g. 4, 7, 10 etc. The tests included are TSH, freeT3, and freeT4.

Toxicity assessment to be done at the beginning of each cycle, at the end of treatment visit and for 30 days after end of treatment.

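### From cycle 2, patients take the Day 1 morning capecitabine dose at home before any required check of the counts and toxicities that could hold it

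*Combined protocol and SAP*

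**What the plan says.** Section 4.1 states: "Patients will be instructed to take the morning dose of capecitabine before coming to clinic for pembrolizumab infusion". The same instruction appears in the Study Summary, section 8.1.11 and section 8.2.5. None of the four places adds a condition, such as waiting for results or for a call from the clinic.

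Section 4.3.1 sends the reader to Tables 2 to 4 for holding or reducing capecitabine:

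- **Table 2** holds the drug for ANC below 1000/mm³ and/or platelets below 100,000/mm³, then "resume at 20% dose reduction".
- **Table 3**, for Grade 3 diarrhea and Grade 3/4 mucositis or esophagitis: "Hold until ≤ grade 1; resume at 20% dose reduction". Grade 2 mucositis or esophagitis is handled the same way.
- **Table 4**, for hand-foot syndrome of Grade 3 or more: "Hold until symptoms resolve to Grade 1 or lower", then resume one level down. Grade 2 is also held, with the reduction left to the treating physician.

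On timing, the section 5.0 schedule puts CBC, chemistry and toxicity assessment at each cycle visit, with a window of 3 days either side. Footnote 14 reads "Toxicity assessment to be done at the beginning of each cycle". Footnote 4, on the CBC, reads "To be performed within 14 days before Day1". Section 4.2.2 says of the medication diary: "This Diary will be reviewed by a member of the study team at every study visit".

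**The concern.** The hold rules can work only if someone knows the counts and grades before the patient swallows the tablets. As written, the patient doses at home and the information may be gathered afterwards in clinic. Two kinds of patient are affected: one who newly meets a hold criterion, and one who first reports at the visit a toxicity that has since resolved but calls for a lower level. Each has already taken that morning's dose at the old level.

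Low counts may give the patient no warning, so section 4.3.1's general duty to withhold does not help when nobody yet knows of the toxicity. What is at stake is the safety of the patients these rules are meant to protect. The primary analysis is not affected, and I claim no material effect on the safety endpoint.

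**Working it through.** This is mainly a question of the order of events, so the first step is to set the texts side by side and ask whether any of them places the checks before the dose.

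1. **Cycle 1 is covered.** Section 3.1.6 requires baseline laboratory tests within 14 days before registration, and treatment cannot start until the patient is registered. The question arises from cycle 2. Holds already in force carry forward and are not at issue.
2. **The visit window.** It permits checks up to 3 days before Day 1 but equally permits them on Day 1 or later. It does not fix the order.
3. **Footnote 14.** The beginning of a cycle includes the Day 1 visit, which follows the home dose.
4. **Footnote 4.** There are two readings.
   - Baseline only: later cycles then have no CBC timing beyond the visit window.
   - Every cycle: the next Day 1 is Day 22 of the current cycle, and 22 − 14 = Day 8, so a Day 8 count would qualify. Days 8 to 14 then leave 7 × 2 = up to 14 capecitabine doses after that count.
   - On either reading the footnote says nothing about toxicity review.
5. **Diary.** It is reviewed at the visit, again after the home dose.
6. **Supply (4.2.2, 8.2.9).** Patients start with 14 days of tablets and are resupplied every 3 weeks, obtaining the tablets from their own pharmacies. Neither section ties resupply to laboratory or toxicity clearance.
7. **Other tests.** Footnote 13 places thyroid tests "prior to the start of the next treatment cycle e.g. 4, 7, 10 etc", and footnote 2 does the same for imaging. No such wording is attached to the tests behind Tables 2 to 4.

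No text closes the gap. The size follows from the dosing schedule (4.2) and the dose levels (4.3.1: 1000, 800 and 640 mg/m²):

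| Quantity | Calculation | Result |
|---|---|---|
| Doses per cycle | 14 days × 2 | 28 |
| Share taken before a Day 1 review | 1 / 28 | 3.6% |
| Planned dose per cycle at full level | 28 × 1000 | 28,000 mg/m² |
| Excess if a hold was due at full level | one dose | 1000 mg/m² |
| Excess if a first reduction was due | 1000 − 800 = 200; 200 / 28,000 | 0.7% of the cycle |
| Planned dose per cycle at level −1 | 28 × 800 | 22,400 mg/m² |
| Excess if a second reduction was due | 800 − 640 = 160; 160 / 22,400 | 0.7% of the cycle |

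The remaining 27 doses can be governed by the Day 1 review.

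On whether the trigger is realistic, section 8.2.10 lists low white cells or platelets, diarrhea and palm or sole rash among effects seen in more than 10% of patients. The platelet entry limit in 3.1.6 (100,000) is also the Table 2 hold threshold, so a patient may enroll at the boundary.

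**The case against.** The strongest reply is about size. The exposure is one dose in 28, it comes after the scheduled rest on Days 15 to 21, and it disappears if the site checks patients before Day 1. The other 27 doses are also taken at home with no routine count between visits, so one check per cycle is simply how this schedule works. All of that is true, and it keeps the point modest. It does not explain why the one check per cycle should be allowed to follow the first dose when it could precede it.

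Several narrower objections have force:

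- Footnotes 2 and 13 may only identify which cycle boundaries get imaging and thyroid tests. The contrast is supporting evidence at most.
- No Day 8 count is scheduled, so the Day 8 case shows what footnote 4 would tolerate, not what is likely to happen.
- The frequencies in 8.2.10 are any-grade. Table 3 makes no change for Grade 1 or 2 diarrhea, and Table 4 none for Grade 1 hand-foot syndrome, so these figures do not give the rate of new holds on Day 1.
- Tables 2 to 4 contain no chemistry trigger. Chemistry matters to capecitabine only through the investigator's discretion over other non-hematologic toxicities.
- The figure of one dose in 28 assumes the review is on Day 1. An earlier review gives none; a later one could give more.
- The medication diary is a separate document and may carry its own instruction.

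None of these supplies a required check before the dose. Good site practice is not a full answer either: section 11.6 requires conduct to follow the approved protocol except in emergencies, so telling a patient to wait would depart from the written instruction.

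**Conclusion.** The concern holds. From cycle 2, a patient who follows the instruction and is checked on Day 1, as the schedule permits, can take a dose that Tables 2 to 4 would have withheld or lowered. The effect is one dose per affected cycle: 1000 mg/m² where a hold was due at full level, or 160 to 200 mg/m² above the correct level where only a reduction was due.

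This assumes that the checks take place on Day 1 and that the criterion was not already known. How many cycles would be affected cannot be estimated, because the documents give no rate of hold criteria newly found on Day 1. The gap is small per event, but it is avoidable and cheap to close, so it should be fixed.

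**What to change.** From cycle 2, adopt one of the following:

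- **(a)** Tell patients to take the Day 1 morning dose only after the clinic has reviewed CBC, chemistry and toxicity and cleared them to dose. This fits the existing 8-hour minimum between doses.
- **(b)** Require those reviews within 3 days before, and not after, the cycle's first capecitabine dose, with clearance given to the patient.

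Option (a) is the simpler. The CBC and toxicity grading are the essential parts of the clearance, since they drive Tables 2 to 4.

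Align the Study Summary, sections 4.1, 8.1.11 and 8.2.5, footnotes 4, 5 and 14, the section 5.0 visit window and the medication diary. State whether the 14 days in footnote 4 apply to baseline only. Hold thresholds and dose levels stay as they are.

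The cost is a wording amendment and a revised diary instruction, with no new tests. The downside is a later morning dose on Day 1 under (a), or a blood draw and contact up to 3 days before the visit under (b).

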### 4.2 Treatment Administration

Agent	Pre-mediations	Dose	Route	Schedule	Cycle Length
Pembrolizumab	n/a	200 mg	IV	Day1 of a 21 day cycle	21 days
Capecitabine	n/a	1000 mg/m 	oral	BID on Days 1-14 every 21 days	

#### 4.2.1 Pembrolizumab

Pembrolizumab is a potent and highly selective humanized monoclonal antibody (mAb) of the IgG4/kappa isotype designed to directly block the interaction between PD-1 and its ligands, PD-L1 and PD-L2. Keytruda™ (pembrolizumab; MK-3475) has recently been approved in the United States for the treatment of patients with unresectable or metastatic melanoma and disease progression following ipilimumab and, if BRAF V600 mutation positive, a BRAF inhibitor.

In this trial, pembrolizumab will be given at a dose of 200 mg IV every 21 days (Day 1 of a 21-day cycle, can be administered +/- 3 days of Day 1) in a 30 minute IV infusion (-5 min/+10 min).

No pre-mediations are required as part of this study. See Section 4.9 for supportive care guidelines for pembrolizumab, including use of corticosteroids.

#### 4.2.2 Capecitabine

Capecitabine is to be self-administered by patient, 1000 mg/m^2 PO BID Days 1-14 every 21 days. It is to be taken preferably 12 hours apart (with minimum 8 hours between doses).It is to be ingested with food or within 30 minutes of eating with 8 oz glass of water (not fruit juices). Tablets are to be swallow whole and not crushed or cut. No supportive medications are required as part of this study.

If dose is missed and next dose would normally be in less than 8 hours, then dose should be skipped entirely and marked accordingly on the medication diary (available as stand-alone document).

Patients will also record doses taken, missed, or skipped, as well as any

occurrence of vomiting, diarrhea, increased stool frequency, or rashes on the Medication Diary. This Diary will be reviewed by a member of the study team at every study visit, and any issues with compliance will be addressed. Along with the diary, patients should bring the medication bottle and any remaining tablets with them on each study visit. The Coordinator and PI will monitor for compliance. If a patient misses more than 7 consecutive doses of capecitabine due to poor adherence, the patient will be removed from study treatment. If capecitabine doses are missed, and it is < 7 doses, they may be made up within the same cycle. Patients will be given 14 days of supply at the start of study treatment. Additional capecitabine tablets will be dispensed every 3 weeks. The consent form will also ask that patients agree to keep the capecitabine pills out of reach from children and other individuals in their home.

#### **4.2.3 Continuation of Investigational Therapy after Radiographic Progression (Pseudoprogression)**

Treatment may be continued in the setting of pseudoprogression (radiographic increase or new lesions felt to be due to inflammation/immune response) as long as all of the following criteria are met:

- Absence of clinical symptoms or signs indicating clinically significant PD.
- No significant decline in Eastern Cooperative Oncology Group (ECOG) performance status.
- Absence of rapid PD or threat to vital organs/critical anatomical sites (eg, spinal cord compression) requiring urgent alternative medical intervention
- Patients are made aware of the potential benefits and risks of continuing study therapy in the setting of Pseudo-Progression.

These patients will continue to be monitored for safety parameters. Patients continuing therapy in the setting of suspected pseudoprogression should continue with treatment according to protocol as long as the above criteria are met and clearly documented in the patient's medical record.

### **4.3 Dose Modifications**

#### **4.3.1 Dose Modification**

Adverse events (both non-serious and serious) associated with pembrolizumab exposure may represent an immunologic etiology. These adverse events may occur shortly after the first dose or several months after the last dose of treatment. Pembrolizumab must be withheld for drug-related toxicities and severe or life-threatening AEs as per Table 1 below. Dose reductions for pembrolizumab are not permitted.

Capecitabine should be withheld/dose reduced for drug-related toxicities and AEs as per Table 2, 3, 4.

See Section 4.9 for supportive care guidelines for pembrolizumab, including use of corticosteroids.

Any patient who receives at least one dose of study therapy will be evaluable for toxicity endpoints. Each patient will be assessed for the

development of toxicity according to the timeframe referenced in the Schedule of Events table). Toxicity will be assessed according to NCI's CTCAE, version 4.03.

Dosing interruptions are permitted in the case of medical / surgical events or logistical reasons not related to study therapy (e.g., elective surgery, unrelated medical events, patient vacation, and/or holidays). Subjects should be placed back on study therapy within 3 weeks of the scheduled interruption of capecitabine and 12 weeks of interruption of pembrolizumab, unless otherwise discussed with the Principal Investigator and QAM. The reason for interruption should be documented in the patient's study record.

If pembrolizumab is held for toxicity, participants are permitted to continue on protocol therapy with capecitabine alone. If capecitabine is held for toxicity, participants are permitted to continue on therapy with pembrolizumab alone.

If capecitabine doses are missed, and it is < 7 doses, they may be made up within the same cycle.

If one drug is permanently withdrawn for toxicity (i.e. the patient cannot dose reduce any further on capecitabine), then the patient should come off study completely.

Capecitabine Dose Reduction Table

Dose Level	Dose
1	1000 mg/m 
-1	800 mg/m 
-2	640 mg/m 
Stop	N/A

